### **5.10.2. Permitted Medications**

All concomitant medications used during the study will be recorded, including the drug generic name, dose amount, route of administration, start date, and stop date.

#### **5.10.2.1. Analgesics**

All analgesics will be collected in the eDiary and recorded in the electronic Case Report Forms (eCRFs).

### **5.10.3. Prohibited Non-Drug Therapies**

Surgical treatment of endometriosis is prohibited from the Week 24/Baseline visit until the patient's final study visit unless urgently needed for patient safety.

## **6. STUDY ASSESSMENTS AND PROCEDURES**

The timing of each study assessment and procedure is provided in the Schedule of Activities (see [Section 1.1](#)). Study procedures are briefly described within [Section 6.5](#). Further details of the procedures are provided in the Study Reference Manual.

### **6.1. Schedule of Observations and Procedures**

Assessments should be completed at the designated visit/time points as described in the Schedule of Activities (see [Section 1.1](#)). The study is divided into 2 periods: Open-Label Treatment Period and Safety Follow-Up Period. Unscheduled visits may occur as needed to evaluate patients.

### **6.2. Open-Label Treatment Period (Week 24/Baseline to Week 52)**

As denoted in the Schedule of Activities (see [Section 1.1](#)), certain Week 24 visit procedures of MVT-601-3101 or MVT-601-3102 will serve as the Week 24/Baseline procedures for patients

who are interested in participating in this extension study, and these Week 24 procedures will be performed under the informed consent for the parent study.

Patients will be required to sign an informed consent form for the extension study, and will be eligible if they meet all of the eligibility criteria.

Once eligibility is determined, all additional Week 24/Baseline visit procedures described in the Schedule of Activities (see [Section 1.1](#)) that were not performed as part of the Week 24 visit of the parent study will be completed. These include the following:

- Informed consent (unless signed previously);
- Record concomitant medications;
- Update the patient's status in the IVRS/IWRS as being in the MVT-601-3103 and receive the lot numbers for study drug allocation;
- Dispense study treatment;
- Dispense or prescribe protocol-specified analgesic drugs;
- Transition the patient within her eDiary from the parent study to MVT-601-3103
- Take study drug dose in clinic; and
- Record adverse events, if any.

The Week 24 visit date in the parent study is defined as the date that the last procedures for the Week 24 visit were completed, acknowledging that the Week 24 visit procedures may be completed on different dates. Patients will have received their last dose of study drug in the parent study on the day prior to the Week 24/Baseline visit, and will receive their first dose of study drug for this extension study in the clinic after the patient is determined to be eligible for this extension study and has provided informed consent to participate. Therefore, results of testing required for eligibility must be available on or prior to the Week 24/Baseline visit.

Patients will continue recording data in their eDiary daily and taking protocol-specified analgesics as needed. Following the Week 24/Baseline visit, on-treatment study visits will occur at Weeks 28, 32, 36, 40, 44, 48, and 52. Sites will monitor diary completion using the TrialManager web portal throughout the study.

Accountability for study drug will be performed at each visit. Instructions for analgesic medication usage will be reinforced at each visit.

Questionnaires are administered on the electronic tablet and on paper at each visit. These procedures should occur before any other types of study procedures are performed. When both electronic tablet and paper questionnaires are required at a visit, the electronic questionnaires should be done first. The order in which the electronic tablet and paper questionnaires should be administered are as follows:

- Electronic tablet questionnaires (in the order they appear in the tablet)
- Paper questionnaires
  - PGA for function
  - EHP Work Domain [Week24/Baseline and Week 52 only]

Patients will bring their eDiary, analgesic medications, and study drug to each visit. The site must document the start and stop dates of the patient's menses.

An endometrial biopsy will have been performed at the parent study Week 24 visit for all patients who participated in MVT-601-3101 (see MVT-601-3101 protocol for details). Safety monitoring for this study includes physical examination, clinical laboratory tests, pregnancy tests, and adverse event collection at each visit. Clinical chemistries will be collected at each visit. A complete blood count will be collected at Week 24/Baseline, Week 28, Week 36, and Week 52. At the Week 24/Baseline visit and Week 52 visit, additional tests include fasting (at least 8 hours, other than water) glucose, lipid profile, and hemoglobin A1c.

ECGs will be done at the Week 24/Baseline and at the Week 52/Early Termination visits. Bone densitometry will occur at the Week 24/Baseline, Week 36, and Week 52/Early Termination visits. Week 52/Early Termination.

Bone densitometry and ECGs will be submitted for central reading.

Study drug compliance will be reviewed at each visit. Fasting (other than water) for at least 8 hours is required prior to blood sampling on Week 24/Baseline and Week 52/Early Termination visits and for 1 hour after administration of the study drug in the clinic. Laboratory requisitions must indicate whether or not the patient was not fasted for their chemistry and lipid testing.

Refer to the Schedule of Activities (see [Section 1.1](#)) for information about study procedures during the Open-Label Treatment Period.

### **6.3. Early Termination Visit and Follow-up Visit**

All patients withdrawing from the study prior to Week 52 will complete an Early Termination visit. The Early Termination visit procedures are identical to those of Week 52; however, for patients whose last dose of study drug is during Week 32 or earlier or within 4 weeks after completion of the Week 36 scan, the bone densitometry does not need to be performed. This procedure may be performed, however, at the investigator's discretion, if it aids in follow-up of an ongoing adverse event(s).

Patients (including those who complete the Week 52 visit and those who withdraw early from this study) will have a Follow-up visit approximately 30 days after the last dose of study drug, or prior to the date of initiation of another investigational agent or hormonal therapy affecting the hypothalamic-pituitary-gonadal axis or surgical intervention or other invasive procedure for endometriosis, whichever occurs first. However, for patients who enroll directly into another relugolix clinical study upon completion of the Week 52 visit, the Follow-up visit may be waived.

The Follow-up visit will be used to assess safety after discontinuation of study treatment including adverse events, clinical safety laboratories, and return of menstruation. Refer to the Schedule of Activities (see [Section 1.1](#)) for individual study visit procedures during the Follow-up visit.

### **6.4. Unscheduled Visits**

Unscheduled visits may be performed at any time during the study whenever necessary to assess for or follow-up on adverse events, at the patient's request, or as deemed necessary by the

investigator. The date and reason for the Unscheduled visit should be recorded in the source documentation. The following activities should be completed at Unscheduled visits: recording of reason for the visit, concomitant medication review, and evaluation of adverse events. In addition, procedures such as vital signs, weight, symptom-directed brief physical examination, central safety laboratory assessment, urine pregnancy testing, pharmacodynamic sampling, 12-lead ECG, study drug compliance and dispensation, eDiary review, dispensation or prescription of protocol-specified analgesics, etc, may be conducted as needed. See the Schedule of Activities ([Section 1.1](#)) for tests that may be performed, as indicated at an Unscheduled visit. The investigator should consult with the medical monitor, if needed, to discuss Unscheduled visit testing. The investigator should obtain approval from the sponsor to perform an unscheduled endometrial biopsy or DXA, unless urgently indicated.

## **6.5. Study Procedures**

### **6.5.1. Efficacy-Related Procedures**

#### **6.5.1.1. Pharmacodynamics Sample Collection**

A blood sample for the pharmacodynamic analysis of serum estradiol will be collected pre-dose at the visits indicated in the study Schedule of Activities (see [Section 1.1](#)), other than at the Week 52 or the Early Termination visit, when no dose is administered. These pharmacodynamic samples will be analyzed at a central laboratory. These results will not be shared with the sites at any time.

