## 1.1. Schedule of Activities

**Table 1-1 Schedule of Activities for Study MVT-601-3103**

PERIOD	OPEN-LABEL TREATMENT									SAFETY FOLLOW-UP
	Week 24/Baseline (Week 24 of Parent Study; Baseline of Extension Study)	Week 28	Week 32	Week 36	Week 40	Week 44	Week 48	Week 52 a (or Early Termination of Study Drug)	Un-scheduled b	Follow-Up c (~30 days after last dose of study drug)
Visit Window (days)	Parent Study Day 169 -10/+20	±7	±7	±7	±7	±7	±7	±7	-	-3 to +18
Informed Consent	X d									
Review Eligibility Criteria	X									
Concomitant Medications e	X f	X	X	X	X	X	X	X	X	X
Vital Signs (BP, HR, Temperature)	X g	X	X	X	X	X	X	X	X h	X
Weight	X g			X				X	X h	
Complete Physical Exam	X g							X	X h	
Visual Acuity i	X g									
Signs and Symptoms-Directed Physical Exam j		X	X	X	X	X	X		X h	X
12-Lead ECG k	X g							X	X h	
Clinical Laboratory Tests l	X g,m	X	X	X	X	X	X	X m	X h	X
Pharmacodynamics Sample n	X g,m							X m	X h,m	
Urinalysis	X g							X	X h	
Pregnancy Test (Urine)	X g	X	X	X	X	X	X	X	X h	X

PERIOD	OPEN-LABEL TREATMENT									SAFETY FOLLOW-UP
	Week 24/Baseline (Week 24 of Parent Study; Baseline of Extension Study)	Week 28	Week 32	Week 36	Week 40	Week 44	Week 48	Week 52 a (or Early Termination of Study Drug)	Un-scheduled b	Follow-Up c (~30 days after last dose of study drug)
Visit Window (days)	Parent Study Day 169 -10/+20	±7	±7	±7	±7	±7	±7	±7	-	-3 to +18
Daily eDiary o	X g	X	X	X	X	X	X	X		X
Site Review of eDiary Data	X g	X	X	X	X	X	X	X	X h	X
Bone Densitometry p	X g			X				X q,r	X h	
Endometrial Biopsy	X g,s								X h	
Dispense Study Treatment	X	X	X	X	X	X	X		X h	
Dispense or prescribe protocol-specified analgesic drugs t	X	X	X	X	X	X	X	X	X h	
Treatment Compliance		X	X	X	X	X	X	X	X h	
Take Study Drug Dose in Clinic	X u							X	X h	
Daily Self-Administration of Study Treatment v		X								
Take Protocol-specified Rescue Analgesics as Needed w		X								

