  - q. This procedure is not required at the Early Termination visit in patients whose last dose of study drug was taken during Week 32 or earlier or within 4 weeks after completion of the Week 36 scan. However, the procedure may be done if it will aid in the evaluation of an ongoing adverse event.
  - r. Patients with a bone mineral density loss of > 3% at their Week 52/Early Termination visit (or most recent scan if the Week 52/Early Termination visit was not done) relative to parent study Baseline measurement will undergo a follow-up bone densitometry scan at 6 ( $\pm$ 1) months and will be contacted to question them about medications and conditions (eg, pregnancy) that might affect bone mineral density through the time of follow-up bone densitometry. The follow-up bone densitometry will be submitted for central reading.
  - s. Endometrial biopsies are to be done per instructions in the parent study. See the Laboratory Manual for guidance on handling and shipping the biopsy sample to the central laboratory for analysis. An endometrial biopsy will have been performed at the parent study Week 24 visit for all patients who participated in MVT-601-3101 only (see MVT-601-3101 protocol for details).
  - t. Please see [Appendix 1](#) for list of protocol-specified analgesics and see the Study Reference Manual for information on where and how to obtain protocol-specified analgesic medications by country. At the Week 52 visit, patients who will not be proceeding to another extension study will be re-dispensed or prescribed protocol-specified analgesic drugs, if needed, to ensure sufficient supply until the Follow-Up visit. For patients proceeding to another extension study, refer to the protocol for that next study.
  - u. Pregnancy test must be negative before the study drug dose is administered.
  - v. Patients will take the first dose of the study drug for this study once daily starting with the Week 24/Baseline visit (taken at the visit). The first dose of study drug for this extension study must not be taken until all parent study Week 24 procedures such as laboratory tests have been completed. Therefore, results of testing required for eligibility (eg, DXA) must be available on or prior to the Week 24/Baseline visit. The last dose of study drug will be taken in the clinic during the Week 52/Early Termination visit.

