
 
To evaluate the pharmacodynamic effects of relugolix 40 mg once daily co-administered with low-dose estradiol and norethindrone acetate for up to 52 weeks, among patients who previously completed a 24-week treatment period in one of the parent studies (MVT-601-3101 or MVT-601-3102), on estradiol.
 
	
 
Change from parent study Baseline to Week 52 in pre-dose concentrations of serum estradiol.
 

Exploratory	

 
To evaluate the benefit of relugolix 40 mg once daily co-administered with low-dose estradiol and norethindrone acetate on endometriosis-associated quality of life (EHP-30 total score), work (EHP Work Domain), and patient-reported quality of life outcomes (European Quality of Life Five-Dimension Five-Level Scale [EQ-5D-5L]) for up to 52-weeks among patients who previously completed a 24-week treatment period in one of the parent studies (MVT-601-3101 or MVT-601-3102).
 
	
 
Change from Baseline to Week 52/EOT in the EHP-30 scale total score;
 
Change from Baseline to Week 52/EOT in the EHP Work Domain score;
 
Change from parent study Baseline to Week 52/EOT in the EQ-5D-5L.
 

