### **5.4. Directions for Administration**

All study patients will take a study treatment of one tablet and one capsule once daily.

The study treatment should be taken in the fasted state (other than water, tea, or coffee) in the morning, at least 1 hour before breakfast. If dosing is missed in the morning for any reason, the study treatment may be taken later in the day, under fasting conditions, at least 1 hour before or 2 hours after eating a meal. The study treatment should be taken as close as possible to the same time of morning each day.

On Week 24/Baseline and Week 52 clinic visit days, study drug will be administered in the clinic rather than at home (see Schedule of Activities in [Section 1.1](#)).

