## **7.8. Pregnancy Reporting**

If any patient becomes pregnant during the study, the site must discontinue the patient from the study treatment immediately and have her return for an Early Termination visit.

If the patient agrees, the investigator should notify the patient's primary care physician of the pregnancy and provide details of the patient's participation in the study and treatment.

A pregnancy is to be reported to the sponsor within 24 hours of awareness by the study site personnel, using the Pregnancy reporting forms and contact information in [Section 7.6](#). The expected date of delivery or expected date of the end of the pregnancy, last menstruation, estimated conception date, pregnancy result, and neonatal data, etc, should be included in this form, as available.

The investigator will follow the medical status of the mother, as well as the fetus, and will report the outcome to the sponsor.

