### **9.4. Efficacy Analyses**

Unless otherwise specified, efficacy analyses will be conducted using the mITT Population.

Efficacy endpoints will be summarized by the original treatment groups assigned in the parent study.

The point estimates and 2-sided 95% confidence intervals (CI) for the primary efficacy endpoints (proportion of responders based on dysmenorrhea NRS scores and use of rescue analgesic medications, proportion of responders based on NMPP scores and use of rescue analgesic medications) will be calculated.

A responder at a given time point and for a specific type of pain (dysmenorrhea or NMPP) is defined as a patient who had a reduction in that type of pain from Baseline greater than or equal to a pre-determined threshold and who did not have an increase in the use of rescue analgesic medications for endometriosis-associated pain compared with the use at Baseline. Patients who had a pain reduction less than the pre-determined threshold or who had an increase in the use of analgesics for endometriosis-associated pain will be considered non-responders. The pain reduction thresholds will be determined for NMPP and dysmenorrhea separately (see the SAP for details) for the parent studies and these same thresholds will be applied to this study.

Baseline values are calculated using the Baseline pain assessment period, which is defined as the period from the date of the first dose of placebo in the parent study Run-In Period through the day prior to the first dose of randomized study drug. Patients' average NRS pain scores and use

of rescue analgesic medications for endometriosis-associated pain (dysmenorrhea or NMPP) will be compared between a given visit-specific pain assessment period (eg, Week 28, Week 32, etc.) and the Baseline pain assessment period. The visit-specific pain assessment period is defined as the last 35 calendar days immediately prior to and including the last dose of study drug treatment received prior to the visit date.

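### Amendment 1 contradicts itself on whether a dose is taken at the Week 52/Early Termination visit, and the conflict reaches the pre-dose estradiol rule and the immediate-stop rules

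*Protocol*

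**What the plan says.** All references are to the protocol as amended by Amendment 1. The sentence in Section 6.5.1.1 is the same in the original protocol.

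- **Section 6.5.1.1** requires the estradiol sample to be pre-dose, "other than at the Week 52 or the Early Termination visit, when no dose is administered".
- **Table 1-1, row** "Take Study Drug Dose in Clinic", is marked at Week 24/Baseline and in the column shared by Week 52 and Early Termination.
- **Table 1-1, footnote v:** "The last dose of study drug will be taken in the clinic during the Week 52/Early Termination visit".
- **Section 5.4:** "On Week 24/Baseline and Week 52 clinic visit days, study drug will be administered in the clinic rather than at home". Early Termination is not named.
- **Section 6.2** requires fasting before blood sampling on "Week 24/Baseline and Week 52/Early Termination visits and for 1 hour after administration of the study drug in the clinic".
- **Table 1-1, footnote n** names Week 52/Early Termination as an estradiol sampling day and requires treatment to follow the sample on every such day.
- **Section 3** gives the only pharmacodynamic endpoint: "Change from parent study Baseline to Week 52 in pre-dose concentrations of serum estradiol".
- **Section 6.3** makes Early Termination procedures identical to Week 52, with bone densitometry the only exception.
- **Section 4.5** stops study drug immediately for listed liver test abnormalities and sends everyone removed from therapy to the Early Termination assessments.
- **Section 7.8**, for pregnancy: "the site must discontinue the patient from the study treatment immediately and have her return for an Early Termination visit".
- **Table 1-1, footnote u** makes a negative pregnancy test a condition of dosing. It is attached to the Week 24/Baseline dose mark only.

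**The concern.** Two things depend on the answer to a simple question: is study drug taken at this visit?

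The first is the estradiol endpoint. The study treatment contains 1.0 mg estradiol, so a sample drawn after the dose would partly reflect the tablet just swallowed. The section that governs sample collection lifts the pre-dose requirement for this one visit, on the ground that nothing is taken there. If that ground is false, the section has removed the rule at the only on-study visit after baseline where the endpoint is scheduled to be measured.

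The second is patient safety. Women who leave treatment early attend a visit that shares its schedule column with Week 52. Some of them have just been told to stop at once. A schedule that shows an in-clinic dose in that column, with no stated exception, conflicts with the instruction to stop.

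**Working it through.** No sample size, power or error rate is involved, so the check is a comparison of passages.

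**Step 1. Is a dose taken at Week 52?**

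| Place | Week 52 | Early Termination |
|---|---|---|
| Section 6.5.1.1 | no | no |
| Table 1-1, in-clinic dose row | yes | yes (shared column) |
| Table 1-1, footnote v | yes | yes |
| Section 6.2, fasting rule | presupposes a dose | presupposes a dose |
| Section 5.4 | yes | not named |

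One section says no and four places say or presuppose yes. The Amendment 1 summary of changes does not list the point.

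**Step 2. What happens to the Week 52 estradiol sample?** There are three cases for a woman who completes treatment.

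1. No dose is taken that day (Section 6.5.1.1 is right). The sample follows the previous day's dose and is in effect pre-dose.
2. A dose is taken and footnote n is followed. The sample is pre-dose.
3. A dose is taken, and the site relies on Section 6.5.1.1 and overlooks footnote n. The sample can be post-dose.

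Only the third case harms the endpoint, and it requires a breach of footnote n. The defect is that two instructions on the same sample disagree.

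**Step 3. What does the text imply at Early Termination?** The dose mark and footnote v both cover Early Termination. Section 6.3 repeats the Week 52 procedures there, and its one exception is not the dose. Section 4.5 sends women removed for any reason to this visit, and Section 7.8 sends pregnant women there after stopping. Taken together, these passages put an in-clinic dose on the schedule of a woman whose treatment has been stopped, which contradicts Sections 4.5 and 7.8. Footnote u does not settle the matter, because it does not attach to this dose mark.

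Other passages point the opposite way. Section 4.5 speaks of assessments, Section 5.4 names Week 52 only, and the densitometry waiver in Section 6.3 assumes that the last dose may have come before the visit. The text is contradictory at Early Termination; it does not amount to one clear order to dose.

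**The case against.** The best case against the point is that its consequences are slight.

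- **Footnote n is the safeguard.** It names this visit and fixes the order of sample and dose. This stands, and it is why the endpoint cannot be called unprotected or the whole pharmacodynamic result called lost. The endpoint is also defined to Week 52, so Early Termination samples are not plainly part of it.
- **The time of the previous dose is already captured.** The eDiary records date and time of study drug administration (Section 6.5.1.2). This stands, and nothing needs to be added.
- **No passage tells a site to dose a woman stopped for pregnancy or liver tests.** The stopping rules are explicit and specific, Table 7-2 repeats immediate withdrawal for pregnancy, and a urine pregnancy test is scheduled at Week 52/Early Termination. A sensible site would follow the stopping rule. This stands as a reason not to read the schedule as a direction to dose. It does not remove the conflict, because footnote v and the dose mark carry no exception.

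A reader might also infer that a clinic dose at Early Termination would shift the analysis windows. For the pain window, Section 9.4 uses "the last 35 calendar days immediately prior to and including the last dose of study drug treatment received prior to the visit date", so a dose on the visit date does not move it. For the treatment-emergent period, Section 9.5 counts 30 days from the last dose. If a dose is in fact taken, that is the right anchor, and moving it back to the decision to stop would drop events that follow real exposure. Neither rule needs changing on this account.

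**Conclusion.** The contradiction is real and can be verified from the text. Section 6.5.1.1 cannot stand beside the dose row, footnote v, Section 5.4 and Section 6.2. Through Section 6.3 and the shared column it extends to a conflict with the immediate-stop rules in Sections 4.5 and 7.8. The Week 52 estradiol endpoint is inconsistently protected: Section 6.5.1.1 waives a requirement that footnote n imposes.

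No bias or number of affected women can be given. The documents state neither how often sites would depart from footnote n nor how many women would stop early for these reasons. The case for correcting the text rests on patient safety and on consistent sampling, not on a computed effect.

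The conclusion applies to Amendment 1. The contents list names Amendments 2, 3 and 3.1, but Amendment 2 is shown only as far as part of its synopsis and the later ones not at all. Whether the conflict survives cannot be checked.

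**What to change.** 1. Reconcile Section 6.5.1.1, the in-clinic dose row, footnotes n, u and v, and Sections 5.4, 6.2, 6.3, 4.5 and 7.8 on whether a dose is taken at Week 52 and, as a separate question, at Early Termination. Which rule is right is for the sponsor to decide.
2. Delete the Week 52/Early Termination exemption from Section 6.5.1.1 so that it agrees with footnote n. This holds whichever way item 1 is settled, because it concerns only the order of sample and dose if a dose is taken.
3. Check whether later amendments already made these changes.

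The cost is wording in one amendment. No procedure, sample, data field or analysis is added.
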